10.1 Regulatory and Ethics Approvals

This study will be conducted in accordance with the protocol and with the following:

- Consensus ethical principles derived from international guidelines including the Declaration of Helsinki
- Applicable ICH Good Clinical Practice (GCP) Guidelines
- Applicable laws and regulations

The protocol, protocol amendments, ICF and other relevant documents (eg, advertisements) must be submitted to an IRB/IEC by the investigator and reviewed and approved by the IRB/IEC before the study is initiated.

- Any amendments to the protocol will require IRB/IEC approval before implementation of changes made to the study design, except for changes necessary to eliminate an immediate hazard to study participants.
- The investigator will be responsible for the following:
 - Providing written summaries of the status of the study to the IRB/IEC annually or more frequently in accordance with the requirements, policies, and procedures established by the IRB/IEC
 - Notifying the IRB/IEC of SAEs or other significant safety findings as required by IRB/IEC procedures
 - Providing oversight of the conduct of the study at the site and adherence to requirements of ICH guidelines, the IRB/IEC, the WHO Good Clinical Laboratory Practice (GCLP), European regulation 536/2014 for clinical studies (if applicable), and with applicable national regulations.

10.2 Informed Consent Process

The investigator or his/her representative will explain the nature of the study to the participant or his/her legally authorized representative and answer all questions regarding the study.

Participants must be informed that their participation is voluntary. Participants or their legally authorized representative will be required to sign and date a statement of informed consent that meets the requirements of the IRB/IEC or study centre.

There must be evidence that written informed consent was obtained before the participant was enrolled in the study and ample time was given to participant to consent. The date the written consent was obtained (as well as the time, ideally) must be recorded. The authorized person obtaining the informed consent must also sign and date the ICF.

Illiterate participants must provide a thumbprint on the ICF and the ICF signed and dated by an impartial witness.

Participants must be re-consented to the most current version of the ICF(s) during their participation in the study.

A copy of the ICF(s) must be provided to the participant or the participant's legally authorized representative.

10.3 Data Protection

Participants will be assigned a unique identifier by the sponsor. Any participant records or datasets that are transferred to the sponsor will contain the identifier only; participant names or any information which would make the participant identifiable will not be transferred.

The participant must be informed that his/her personal study-related data will be used by the sponsor in accordance with local data protection law. The level of disclosure must also be explained to the participant.

The participant must be informed that his/her medical records may be examined by Clinical Quality Assurance auditors or other authorized personnel appointed by the sponsor, by appropriate IRB/IEC members, and by inspectors from regulatory authorities.

10.4 Other Ethical Considerations

Following completion of study procedures, any remaining samples will be stored temporarily in case further testing for this study is deemed to be necessary. Samples will be labelled with a study identifier and date of collection; the specimens will be linked to results of other mycobacteriology tests, the final study diagnosis for each

sample (e.g. drug-resistant, drug-sensitive, indeterminant for each drug compound). Samples will be stored temporarily (up to 2 years) at the sites. Further testing may be required at a Reference Laboratory or specialized research laboratories abroad. An export permit will be obtained accordingly when possible.

In the event that one site does not meet sample processing targets within the study timelines, the study will go forward at the other sites and the investigators will proceed with data submission as per study plan.

11 Data Handling and Record Keeping

All participant data relating to the study will be recorded on printed or electronic CRF unless transmitted to the sponsor or designee electronically (e.g., laboratory data). The investigator is responsible for verifying that data entries are accurate and correct by physically or electronically signing the CRF.

The investigator must maintain accurate documentation (source data) that supports the information entered in the CRF.

The investigator must permit study-related monitoring, audits, IRB/IEC review, and regulatory agency inspections and provide direct access to source data documents.

The sponsor or designee is responsible for the data management of this study including quality checking of the data.

Study monitors will perform source data verification to confirm that data entered into the CRF by authorized site personnel are accurate, complete, and verifiable from source documents; that the safety and rights of participants are being protected; and that the study is being conducted in accordance with the currently approved protocol and any other study agreements, ICH GCP, and all applicable regulatory requirements.

Records and documents, including signed ICFs, pertaining to the conduct of this study must be retained by the investigator for 2 years after study completion unless local regulations or institutional policies require a longer retention period. No records may be destroyed during the retention period without the written approval of the sponsor. No records may be transferred to another location or party without written notification to the sponsor.

11.1 Source Data and Source Documents

Source documents provide evidence for the existence of the participant and substantiate the integrity of the data collected. Source documents are filed at the investigator's site and may include:

- Xpert MTB/XDR test results (electronic)
- Xpert MTB/RIF test results (electronic)

- Xpert MTB/RIF Ultra test results (electronic)
- Hain MTBDR*plus* and MTBDR*s* test strips
- NGS results (electronic records)
- Manually-collected data such as lab requisitions, lab registers, and laboratory worksheets (AFB smear log, DST worksheets, QC records, etc.)
- Data generated from additional, automated instruments; e.g., MGIT unloaded positive, negative, and DST reports

Data reported on the CRF or entered in the eCRF that are transcribed from source documents must be consistent with the source documents or the discrepancies must be explained. The investigator may need to request previous medical records or reports (if available), depending on the study.

The investigator/institution should maintain adequate and accurate source documents and trial records that include all pertinent observations on each of the site's trials subjects. Source data should be attributable, legible, contemporaneous, original, accurate and complete. Changes to source data should be traceable, should not obscure the original entry and should be explained if necessary.

11.2 Data Management

For the clinical study, de-identified sample CRF data will consist of participant medical history, clinical examination, and prior laboratory testing results when available. All clinical CRF notes will be transferred to the eCRF by Data Entry Clerks.

All laboratory results (smear, culture, DST, molecular results) will be recorded by laboratory technicians directly on the laboratory CRF. All Xpert testing will generate electronic records of test results. All electronic results will be stored electronically on password-protected computers at the site. Data will also be transcribed into the CRF. LPA testing will generate results on paper test strips. These test strips will be interpreted by the operator and input into the laboratory CRF. All LPA test strips will be retained by the site as source documents. Laboratory CRFs will be transferred from paper CRFs to eCRFs by Data Entry Clerks at the sites and uploaded to the Openclinica study database. The OpenClinica Community v3.13 database is password controlled and restricted. FIND will ultimately be responsible for data management.

Electronic double-data entry must be conducted by two on-site Data Entry Clerks. Data entry training will be provided by FIND, either on site or remotely. Sites will use a password-protected web-based data-entry tool which has the advantage that study monitors will have continuous access to the electronic data. Electronic data will be backed up daily.

Where possible, first data entry will be done as soon as a result becomes available (real-time). Second data entry will only be done by study staff after all sample results

(culture, NGS, Xpert) are available. The Principal Investigator of each site will review all data entered for the site's samples.

Details relating to data entry procedures and timelines will be provided to the sites in a data management user manual.

Study monitors will conduct regular checks to see that all paper and electronic records are consistent and accurate. A priority during monitoring visits will be to ensure correctness of electronic data entries in comparison to source data.

Additional details relating to data entry procedures and timelines will be provided to the sites in the data management SOP.

12 Quality Management

Quality Management for this study consists of Quality Control activities, training and capacity building provided by FIND (or designee) to the investigational sites and laboratories, as well as the use of Standard Operating Procedures, Work Instructions, Tools and Templates.

Training on the protocol, GCP and the use of the IVDs and laboratory tests will be provided by FIND. A Laboratory Manual which describes all of the sample testing procedures will be provided by FIND prior to the commencement of the study. Training on the EDC system will be provided by FIND Data Management prior to first participant enrolment.

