5.3.2 Index Test

The Xpert MTB/XDR assay detects Mtb mutations associated with INH, ETH and second-line drug resistance direct from sputum. In line with this intended use, clinical samples will be directly tested by the Xpert MTB/XDR assay. However, the assay will also be used to test the culture isolate. This additional Xpert MTB/XDR assay testing will allow for a comparison of performance and non-determinant rates between testing directly from the sample and testing from the culture isolate. It will also support resolution of potential discordant LPA and NGS results from the initial Xpert MTB/XDR test result, as these tests will also be performed from the culture isolate (discordance may arise as a result of infections with a mix of different strains, with only one strain being grown out in culture). Furthermore, as all assays will be performed on the same culture, there is also no risk of any assay being tested on a different quality sample.

Review bias will be avoided in this study as the index test requires no manual interpretation by the operator. All results are automatically generated by the GeneXpert instrument and will be directly recorded by the operator on the laboratory case report form (CRF).

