6.1.2 Study Workflow

Study flow is shown in Figure 1. All available Xpert MTB/RIF TB-positive samples will be tested in this study (i.e. consecutive patient samples) until sample size targets are met. All molecular assays will be performed in accordance with SOPs provided by the manufacturers. Specimen handling and processing by routine tests will be carried out according to NTP local policies and standards.

Samples will first be tested by Xpert MTB/RIF or Ultra, as part of routine diagnostic procedures. This Xpert MTB/RIF step will act as a screening tool for trial enrolment. Participants testing positive for MTB by Xpert MTB/RIF will be asked to volunteer for the Xpert MTB/XDR trial. This (testing of specimens from TB-positive samples) is in line with the intended use of the XDR assay as an add-on test to the Xpert MTB/RIF assay.

[figure not shown]
A staged enrolment will proceed: Stage 1 will enrol 360 MTB-positive participants, irrespective of RIF resistance/sensitivity. Once enrolment is complete, Stage 2 will enrol 400 MTB-positive RIF-resistant participants (see section 9.1 and Appendix 4: Sample Requirement to Achieve Target Sample Size). This staging is designed to better evaluate Xpert MTB/XDR sensitivity for second-line resistance detection.

In order to efficiently assess the diagnostic performance of the Xpert MTB/XDR assay, participants will be asked to provide ≥ 3 ml of sputum (either a single sputum or two consecutively collected and pooled sputa). Samples will be homogenized and split for testing.

The Xpert MTB/XDR assay and acid-fast bacilli smear will be performed on the direct sample. 2ml of sputum will be decontaminated and used for MGIT and LJ culture.

Following direct testing, phenotypic MGIT DST will be performed for all culture-positive samples for INH, RIF, fluoroquinolone (moxifloxacin and levofloxacin), AMK, ETH (ethionamide), KAN and CAP. Cultured samples will also undergo subsequent molecular testing by LPA and targeted NGS of relevant gene regions (*katG*, *inhA*, *fabG1*, *ahpC*, *gyrA*, *gyrB*, *rrs*, and *eis*) and another Xpert MTB/XDR assay. NGS will be performed from the culture isolate to obtain sequencing reads of high quality.

Figure 1. Phase II sample flow

≥ 3ml of sputum is required for the trial. This can be achieved through an individual sputum or pooling of serially collected sputa, homogenized with glass beads.

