All diagnostic test results (smear, Xpert MTB/XDR on direct sample, MGIT, LJ, Xpert MTB/XDR on culture isolate, MTBDR*plus*, MTBDR*sl*, DST and NGS results) will be recorded by the laboratory technicians for each site on the laboratory CRF.

7 Specimen Collection, Handling, Transport and Storage

Clinical (sputum) samples from enrolled patients will be used in this study. Patients will be asked to provide up to two sputum samples for testing after providing informed consent for the study. Sputum samples from the same patient will be pooled and used directly for acid-fast bacilli smear, Xpert MTB/XDR and MGIT and LJ culture.

Appropriate laboratory staff at each site reference laboratory are responsible for receiving the samples, storing the samples and conducting all testing in line with BSL3 requirements. All leftover samples must be stored until study conclusion and completion of all analyses, in case any additional or repeat testing is requested by the sponsor.

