7.1 Reference Standard Test and Index Test Procedures

A composite reference standard of phenotypic DST and NGS will be used for resistance detection to ensure high confidence in the reference standard for this study. Phenotypic MGIT DST and targeted NGS will be performed on the culture isolate for each clinical sample. MGIT DST will be done on site to determine culture drug-susceptibility to INH, ETH, moxifloxacin, levofloxacin, AMK, KAN and CAP at the revised WHO critical concentrations¹⁵. Targeted NGS of the gene regions included in the Xpert MTB/XDR assay will be performed on DNA extracted from the cultured sample, which will be sent to a SNRL for NGS, or sequenced locally using primers specific for the gene regions included in the assay. The output for both phenotypic DST and NGS results are automated, and require no manual operator interpretation. Testing results, when obtained, will be input onto the laboratory CRF.

The index test will be performed on both the direct clinical sample as well as the culture isolate, to ensure high Xpert MTB/XDR diagnostic performance direct from sputum and to provide a basis for comparison if any discordants are seen between the initial Xpert MTB/XDR result and the phenotypic DST and additional molecular test results (NGS and LPA). The output for the Xpert MTB/XDR assay is automated and does not require manual interpretation. As with the reference test, all Xpert test results will be noted on the laboratory CRF.

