12.1 Quality Control

Quality control should be applied to each stage of data handling to ensure that all data are reliable and have been processed correctly. The investigational site is responsible for performing regular Quality Control checks on the data they generate. Additionally, the sponsor will perform risk based monitoring of this study, and associated Quality Control checks, as described in the Monitoring Plan.

QC will be applied to each stage of data handling to ensure that all data are reliable and have been processed correctly:

- Laboratory staff will be trained in data collection and entry
- All source documentation will be filed and preserved
- All assay results will be recorded onto paper laboratory CRFs immediately following testing
- All data will be double entered from the paper CRF to the eCRF by two on-site staff
- Electronic data will be backed up daily
- The Co-investigator will review all data entered for the site's samples

- The Trial Manager and Data Manager will perform periodic data checks to ensure all paper and electronic records are complete and input data are consistent and accurate

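### Neither document masks the reader of the MTBDRplus and MTBDRsl strips, and the direct Xpert MTB/XDR result will normally already be on the laboratory CRF, so the secondary Xpert v LPA comparison is open to review bias

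*Protocol*

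**What the plan says.** Protocol 6.1.2 sets the order of testing. At the start, "The Xpert MTB/XDR assay and acid-fast bacilli smear will be performed on the direct sample". Culture and phenotypic DST follow, and then "Cultured samples will also undergo subsequent molecular testing by LPA and targeted NGS of relevant gene regions", together with a second Xpert MTB/XDR run on the isolate. The same section lists every test result, including both Xpert results and both LPAs, and says that they "will be recorded by the laboratory technicians for each site on the laboratory CRF". Protocol 12.1 adds the timing: "All assay results will be recorded onto paper laboratory CRFs immediately following testing".

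On how the LPA is read, Protocol 11.2 states: "These test strips will be interpreted by the operator and input into the laboratory CRF". It also has the sites keep the strips.

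On review bias, Protocol 5.3.2 (Index Test) states: "Review bias will be avoided in this study as the index test requires no manual interpretation by the operator". Protocol 7.1 says of the reference tests: "The output for both phenotypic DST and NGS results are automated, and require no manual operator interpretation". It says the same of the Xpert output.

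The Xpert v LPA comparison is part of secondary objective 2.1 (Protocol section 2 and 9.2.3; SAP 4.3). Protocol 9.2 also compares the failure and invalid rates of Xpert with those of the LPAs, descriptively.

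**The concern.** The two LPAs are the comparators, and of the index, reference and comparator tests they are the only ones that the protocol describes as needing interpretation by a person. Under Protocol Appendix 5 the call depends on judging whether mutant-probe bands are present or wild-type bands are absent. A reader who knows the Xpert result may let it settle a faint band.

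If that happened, LPA calls would drift towards Xpert, and a real difference between the assays, in either direction, would shrink. A strip that ought to be reported as uninterpretable could also be turned into a call, which would lower the LPA invalid rate. How the new cartridge compares with the LPAs is one of the questions that Protocol 3.2 sets for this phase.

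**Working it through.** **Step 1: is the Xpert result on record when the strip is read?** Four statements bear on this.

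- Direct Xpert MTB/XDR is run on sputum; the LPA is run later, on the culture isolate (Protocol 6.1.2).
- The operator enters the Xpert result on the laboratory CRF (5.3.2).
- Entry is made straight after each test (12.1).
- LPA calls go on the laboratory CRF as well (6.1.2, 11.2).

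Together these mean that the direct Xpert result will normally have been recorded before the strip is read. The same cannot be said of the isolate Xpert run or of DST, because their timing relative to the strip reading is not fixed.

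**Step 2: does any stated safeguard reach the strip reader?**

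- Protocol 5.3.2 and 7.1 rely on automated output for Xpert, phenotypic DST and NGS. The LPA is not automated.
- Protocol 5.3.3 covers comparators in its title but does not say how they are read.
- The only mention of masking in either document concerns the interim analysis (Protocol 9.3).
- Double data entry (11.2, 12.1) copies the paper call into the database; it does not re-read the strip.
- Strips are kept, so a re-read is possible, but none is planned.
- Appendix 5 gives Xpert an indeterminate and a non-determinate category. For the LPAs it defines only sensitive and resistant, so an equivocal strip has no category of its own.

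**Step 3: which results are exposed?** The composite reference standard is phenotypic DST plus NGS (Protocol Table 1 and 9.2.2; SAP sections 12 and 16). The LPA is not part of it, so Xpert sensitivity and specificity against the composite do not depend on any strip reading. The exposed results are the Xpert v LPA part of objective 2.1 and the LPA failure and invalid rates.

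**Step 4: how much does one call weigh?** The plan gives no figure on this point and no rate of equivocal strips. What can be computed is the weight of a single call in LPA sensitivity, 100/n percentage points. Here n is the expected number of resistant samples from Protocol Appendix 4 (MTB-positive group plus RIF-resistant group), which matches Table 2. This takes the LPA as scored against the composite standard on the same samples.

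| Drug | n | One call (100/n) | Three calls (300/n) |
|---|---|---|---|
| INH | 82 + 313 = 395 | 0.25 | 0.8 |
| FQ | 14 + 79 = 93 | 1.1 | 3.2 |
| KAN | 3 + 68 = 71 | 1.4 | 4.2 |
| AMK or CAP | 6 + 28 = 34 | 2.9 | 8.8 |

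Table 2 has no ETH row, so no figure can be given for ETH. As a check on the inputs, the Wilson interval with continuity correction at 90% gives 73.7 to 97.1 for n=34 (Table 2: 74 to 97) and 81.6 to 95.0 for n=93 (Table 2: 82 to 95).

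**The case against.** Several points on the other side have weight.

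- **The review-bias sentence is about the index test.** It sits under that heading and gives only the automation of the index test as its reason. A reader might infer that the protocol promises an Xpert v LPA comparison free of review bias and then contradicts itself. It does not: no passage claims that strip reading is masked. The sentence speaks loosely of the study as a whole, and its reasoning stops at the index test. This stands.
- **The CRF layout is not shown.** A reader might infer that the technician has the Xpert result in front of them, or is the person who ran it. The documents establish only that the result will normally have been recorded. A separate LPA page may already exist. This stands.
- **Other documents may deal with it.** Protocol 5.1 refers to SOPs and section 12 to a Laboratory Manual, and strip-reading procedure could be set there. This stands, but the protocol and SAP should not be silent on it.
- **The mechanism is not demonstrated.** Appendix 5 gives a categorical band rule, and nothing in the documents shows how often a strip is equivocal or which way a reader would lean. This stands as a limit on size. It does not remove the opening for bias, since the rule still has to be applied by a person.
- **The stakes are limited and errors are recoverable.** The comparison is secondary, no hypotheses are tested (SAP section 8), and the strips are kept. This is correct and is a reason to keep the change small. Recovery by re-reading works only if someone plans it.

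**Conclusion.** The point holds as a gap in the plan: strip reading depends on an operator, the direct Xpert result is normally recorded first, and neither document masks the reader. It bears on the secondary Xpert v LPA comparison and the descriptive LPA failure and invalid rates.

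Two stronger conclusions are tempting and should not be drawn. The first is that the study's main accuracy estimates are compromised; they are not, because the LPA is outside the composite standard. The second is that the per-call figures estimate the bias. They are the weight of one sample and would be the same for an error from any cause. To say, for example, that two swayed AMK strips hide a 5.9-point difference (2/34) assumes that the difference exists, that two strips are equivocal and that both are read Xpert's way. The documents support none of these assumptions. Size and direction remain unknown.

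The conclusion assumes that the order of testing and recording in Protocol 6.1.2 and 12.1 is followed, and that no SOP or manual already masks the reader. On that footing this is a worthwhile, low-cost improvement and not a fault in the primary analysis.

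**What to change.** In Protocol 11.2 and 6.1.2, require MTBDRplus and MTBDRsl strips to be read and signed on a separate LPA page that does not show the Xpert, DST or NGS results. The page should be completed before it is joined to the rest of the laboratory CRF. Where existing staffing allows, the reader should be a technician who did not run that patient's Xpert test. This part should stay optional, because the documents do not set out how bench tasks are divided.

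In Protocol 5.3.2, limit the review-bias statement to the index test.

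If the SOPs or the Laboratory Manual already mask the reader, one sentence in 11.2 saying so would replace the new page. If the page cannot be introduced, a masked re-read of the retained strips is the fallback.

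The cost is one extra CRF page and some bench scheduling, with no additional tests.
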